8.6.5 Management of Pregnancy Exposure Cases

The Investigator is expected to record in the provided "Pregnancy Exposure Report Form" any case of pregnancy exposure occurring in a female patient or in a patient's partner enrolled on the study while participating in the study, occurring during the treatment and follow-up periods. This form will be sent by email to the Sponsor's DSM within 5 days after the Investigator became aware of the pregnancy.

The "Pregnancy Exposure Report Forms" are distributed to the sites to be used for this purpose.

The Investigator is requested to follow each case of pregnancy exposure until the outcome, provided that the female patient or the female partner of a male patient enrolled in the study has signed the related pregnancy ICF..

The form will be sent to the Sponsor's DSM by email within 5 days after the Investigator became aware of the pregnancy and is to also be fully completed and sent again within 5 days after the outcome is known.

If the pregnancy results in an abnormal outcome, this will be recorded in the eCRF as an SAE and managed as described in Section 8.6.3.1.

8.6.6 Annual Safety Reporting

Once a year throughout the clinical study, the Sponsor will submit to the concerned national CAs and ECs a safety report (Development Safety Update Report, DSUR), taking into account all new safety information received during the reporting period.

8.6.7 Breaking of the Randomisation Code

Breaking of the Randomisation Code procedure is not applicable to this study.

8.6.8 Serious and Non-Serious Adverse Events Follow-up

After the End of Study Visit or 28 days after last study drug administration whichever occurs last, the Investigator is not requested to actively follow-up the patient unless ongoing SAEs or non-serious AEs of special interest (as per Cohort Review Committee) are present. However, if after the end of the study the Investigator becomes aware of any reportable SAEs, they should be duly reported to the Sponsor. These SAEs should be recorded in the eCRF if it is available. If the eCRF is not available, the paper SAE report form will be used as a backup.

Patients who discontinued the treatment for safety reason will be followed until the event disappears, the patient's condition stabilizes, or until recovery from all toxic effects and longer in case of expected delayed toxicity.

8.7 COHORT REVIEW COMMITTEE

A CRC consisting of the Principal Investigators and the Sponsor's qualified Medical Representatives (and invited experts when needed) will conduct an ongoing review of the safety, PK, and PD data. Specifically, in both Step 1 and Step 2, the CRC will assess all the available data at the end of each dose-level and will confirm the dose-escalation as per the protocol or any incremental dose adjustments, if needed. In addition the CRC has the duty to drive any adjustment in premedication and concomitant medication. The CRC decision will be immediately implemented and notify to the CA/EC when appropriate. At the time the Step 2 starts, the CRC will include investigators experts in the field of NHL.

Appropriate representatives of the Sponsor and the coordinating CRO will also attend and document the outcome of the meeting.

The Committee will meet by telephone (or in person if possible) to review all available data pertaining to patient safety, PK, and PD (if any) data prior to dose-escalation to a subsequent cohort, and at other times as needed. Data will be provided as described in the approved Data Review Plan. Decisions of the CRC will be documented and sent to the sites.

Roles and responsibilities of CRC as well as meeting schedule and format of information are set in a separate Cohort Review Committee Charter.

9. STATISTICAL METHODS AND DETERMINATION OF SAMPLE SIZE

9.1 DETERMINATION OF SAMPLE SIZE

As first estimation, approximately 122 evaluable patients are expected to be enrolled in the study: 100 in Step 1 and 22 in Step 2; however, the total number of evaluable patients depends upon the number of doses and patients by dose cohorts to establish the MTD in Step 1 and Step 2.

It is anticipated that approximately 20% of patients will not pass successfully the Screening Visit. Patients who drop out prior to be evaluable for DLT during the dose escalation will be replaced.

9.2 ANALYSIS POPULATIONS

The following analysis population will be considered in the statistical analysis:

- **DLT population**

All patients receiving at least 75% of the first scheduled study drug administration and with a safety follow-up of 21 days after the administration. Patients enrolled in the dose escalation phase who are not DLT evaluable will be replaced.

- **Safety population**

All patients receiving at least 1 dose of study treatment.

- **Efficacy population**

All eligible patients who receive at least 2 complete treatment cycles and have at least 1 disease assessment are to be considered evaluable for efficacy.

- **Per-Protocol (PP) population**

All patients of the efficacy population excluding patients who experience major protocol violation(s) that may affect the efficacy analyses.

- **PK population**

All patients receiving study treatment and with reliable drug assay data relevant for the PK parameter of interest.

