| Safety Endpoints | 
Incidence, intensity, CTCAE version 4.03 grading, seriousness and treatment-causality of Treatment Emergent Adverse Events (TEAEs).Frequency of clinically significant abnormalities in physical examination, safety laboratory tests, urinalysis, vital signs, and 12-Lead ECG record. |
| Sample size | 
As first estimation, approximately 122 evaluable patients are expected to be enrolled in the study: 100 in Step 1 and 22 in Step 2; however, the total number of evaluable patients depends upon the number of doses and patients by dose cohorts to establish the MTD in Step 1 and Step 2.
 
It is anticipated that approximately 20% of patients will not pass successfully the Screening Visit.
 
Patients who drop out prior to be evaluable for DLT during the dose escalation will be replaced.
 |
| Analysis populations | 
DLT population All patients receiving at least 75% of the first scheduled study drug administration and with a safety follow-up of 21 days after the administration. Patients enrolled in the dose escalation phase who are not DLT evaluable will be replaced.Safety population All patients receiving at least 1 dose of study treatment.Efficacy population All eligible patients who receive at least 2 complete treatment cycles and have at least 1 disease assessment are to be considered evaluable for efficacy. |

| | |
|-----------------------------|---|
| | 
▪ Per Protocol population All patients of the efficacy population excluding patients who experience major protocol violation(s) that may affect the efficacy analyses.▪ PK population All patients receiving study treatment and with reliable drug assay data relevant for the PK parameter of interest. |

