At the time Protocol Version 3.0 is running, the dose cohort of 1.60 mg/kg has been successfully completed in Step 1, therefore the dose escalation in Step 2 will start at 0.80 mg/kg (or at lower level as per decision of the CRC).

In both Step 1 and Step 2, if 2 or more patients experience a DLT at any dose level, further enrolment at that dose level and further dose escalation will cease, and the previous dose level will be defined as the MTD. However, if ≥ 2 DLTs occur during the dose escalation, an intermediate dose level can be evaluated prior to defining the previous dose level as MTD. Upon MTD definition, the MTD cohort in both Step 1 and Step 2 will be expanded up to a total of 10 patients to further explore the safety profile of MEN1309.

In both Step 1 or Step 2, each dose level escalation (or de-escalation) at the pre-defined dose level of MEN1309 or at any intermediate dose levels will be subject to the assessment of the CRC which consists of the Principal Investigators and the Sponsor's qualified Medical Representatives (and invited experts when needed). In addition the CRC has the duty to drive any adjustment in premedication and concomitant medication. The CRC decisions will be immediately implemented and notify to the CA/EC, when appropriate. At the time the Step 2 is open, the CRC will include investigators who are experts in the field of NHL.

The overall study duration will depend on the number of escalating dose levels/cohorts and the number of patients by cohort, as described in the above sections.

All patients will undergo a 12-week Pre-Screening Period followed by a 4-week Screening Period. The Pre-screening Period in patients who are CD205 positive can be extended up to the time they undergo the Screening Visit.

Each treatment cycle will last approximately 3 weeks.

Individual study duration will depend on the duration of study treatment which continues up to disease progression for solid tumors and up to 8 cycles for NHL (further cycles beyond the 8th cycle may be allowed for patients who still benefit from the treatment based upon the Investigator's medical judgement and medical monitor approval).

The End of Study Visit will be performed within 6 weeks after the last administered dose or at the time of study withdrawal/treatment discontinuation of study drug.

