8.2.3 Withdrawal of patients from study or discontinuation of study drug

Participation in the study is strictly voluntary and patients have the right to withdraw from the study at any time without explanation. This will not affect their rights for future medical care.

Patients may also be discontinued from study drug at the Investigator's discretion or at specific Sponsor's request at any time. Patients will be withdrawn from the study if they experience:

- Protocol violation (e.g., prohibited medication, poor compliance with study procedures/treatment).
- Disease progression.
- DLT at Cycle 1.
- Occurrence of any of the ADR criteria qualifying for DLT at any Cycle following Cycle 1.
- Life threatening related Serious Adverse Event (SAE).
- Patient receives other treatment for solid tumors or lymphoma.
- Occurrence of pregnancy.
- Patient's request.

NOTE: Patients who experienced DLT might be allowed to continue on study at a lower dose if considered beneficial by the investigator and after approval by the Sponsor.

All patients shall undergo the End of Study Visit at the time of study withdrawal or discontinuation of study drug. Unscheduled assessments showing disease progression and leading to patient's withdrawal can replace the End of Study Visit provided that all assessment/procedures scheduled for this visit are completed.

If a patient prematurely terminates the study as per patient's request, data already collected will be used and analyzed for the purpose of the study, as per local regulation.

In case of withdrawal of consent, the patient may choose if samples/images which are already collected but not analysed yet, can be analysed or shall be destroyed.

During escalation phase, patients not evaluable per DLT will be replaced.

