8.3.3 Drug accountability

Upon receipt of all IMP, study site personnel or the designated pharmacist will open the shipment package, verify the contents as stated on the enclosed shipping form, and confirm the receipt by filling in and sending the form “Handing over and delivery receipt of Investigational Medicinal Product” to the Department of Pharmaceutical Development of A. Menarini Research & Business Service GmbH.

The Investigator will be responsible for documenting the dispensing of the IMP to the patient by entering the unique vial number in the source documents and in the eCRF.

The amount of administered drug product will be documented by the Investigator in the source documents and in the eCRF in order to allow for drug accountability.

In addition, the sites will maintain paper drug accountability forms to document dispensed IMP per patient. The peel-off labels of the vials will be pasted onto these paper drug accountability forms.

NOTE: In case of incomplete administration of study treatment because of the occurrence of treatment-related SAE/DLT, the remaining infusion solution has to be stored in a refrigerator at (2 to 8°C) for 48 hours and shall be sent to A. Menarini Research & Business Service GmbH according to the instructions provided in the Clinical Trial Medication Manual (CTM). The remaining infusion solution must be kept in a secure area, out of reach and sight of children and inaccessible to any unauthorized individuals.

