8.5.5 Study Endpoints

8.5.5.1 Primary Endpoint

Identification of MTD, defined as the highest dose level at which no more than 1 of 6 patients experiences a DLT during the DLT assessment window. In case the prophylactic use of growth factor support is made mandatory by the CRC, MTD with growth factor support will be established. **Identification of DLT**, defined as any of the following adverse drug reactions (ADRs) that will be assessed during Cycle 1:

- any grade ≥ 3 cardiac toxicity, new segmental wall-motion abnormalities, or cardiac troponin I or T elevation of grade 3 or higher;
- any grade ≥ 3 elevations in total bilirubin, hepatic transaminases, or ALP levels; in patients with baseline grade 2 hepatic transaminase or ALP levels, an elevation to $\geq 10 \times$ ULN is considered a DLT;
- any grade 3 non-haematologic toxicity lasting > 7 days, (excluding diarrhea/nausea for which no adequate and optimal therapy has been implemented and alopecia);
- any grade 3 vomiting lasting > 3 days despite adequate and optimal therapy;
- any grade ≥ 4 non-haematologic toxicity;
- any grade 4 thrombocytopenia or anemia;
- any grade 4 neutropenia lasting > 7 days or febrile neutropenia;
- any treatment delay of > 2 weeks because of delayed recovery from toxicity related to MEN1309 (except for alopecia).

In case neutropenia will be established as the only DLT, the study will continue with the assessment of DLT of MEN1309 given together with routine prophylaxis with growth factors.

Upon the prophylactic use of growth factor support for neutropenia is made mandatory by the CRC, the DLT criterion related to grade 4 neutropenia will change as follows:

- any grade 4 neutropenia lasting > 5 days or febrile neutropenia despite the use of growth factor support.

Although dose escalation is primarily based on the incidence of DLTs during Cycle 1, toxicities that

meet criteria for DLTs and are observed during Cycle 2 or subsequent cycles are also taken into account for the assessment of toxicity and definition of MTD.

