Demographic and baseline characteristics, including age, gender, race will be summarized by cohort. All demographic data recorded on the eCRF will be listed.

Medical History and Concurrent Medical Conditions

Medical history will be coded using the Medical Dictionary for Regulatory Activities (MedDRA version 15.1). The number of patients with at least one recorded medical history or current medical condition will be presented using frequency counts and percentages as well as an incidence table by System Organ Class (SOC) and Preferred Term (PT). The safety population will be used for this summary. Details of medical history will be provided in listings.

Safety Analyses

Safety evaluations will be performed using the safety population.

Adverse Events

AEs will be categorized as Treatment-Emergent Signs and Symptoms (TESS) or Non-TESS for each of the study periods defined below. If an AE occurs for the first time or if it worsens in terms of seriousness or severity after the first study drug intake, it will be classified as TESS, otherwise it will be classified as non-TESS. Each adverse event will be classified according to the grade (Grade 1 to 6) depending on severity of the event, as specified in Section 8.6.1.5 of the Study Protocol.

The following periods are defined for assignment of TESS:

- Cycle 1: date of the administration to the day before the administration of Cycle 2 or, if the subject is discontinued, until the end of study.
- Cycle n: date of the administration to the day before start of Cycle n+1.

The following rule will be applied for each period: Period start date \leq AE start date \leq Period stop date.

The maximum relationship to study drug will be reported for the respective summaries. All AEs summaries will be based on the Safety population.

In particular grade ≥ 2 ADR will be listed since the occurrence of grade ≥ 2 ADR is associated with the switch from an ATD design to a 3+3 design.

The intensity of an adverse event is reported on the eCRF using the following definitions:

- **Mild:** It does not interfere with routine activities;
- **Moderate:** It interferes with routine activities;
- **Severe:** It makes it impossible to perform routine activities.

The maximum intensity will be used for the summaries; all events will be included in the listings.

Missing intensity will be left as missing and categorised as such.

Serious Adverse Events (SAEs) are defined in Section 8.6.3 of the Study Protocol

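### The DLT population has no clause that keeps a patient with a DLT evaluable, and no analysis set is named for the MTD count

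*Protocol*

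**What the plan says.** Protocol 9.2, the synopsis and SAP 6.1.1.3 define the DLT population in the same words: "All patients receiving at least 75% of the first scheduled study drug administration and with a safety follow-up of 21 days after the administration". Both conditions must be met. The sentence that follows in each place is "Patients enrolled in the dose escalation phase who are not DLT evaluable will be replaced". Protocol 8.2.3 repeats it: "During escalation phase, patients not evaluable per DLT will be replaced". Protocol 9.1 and SAP 6.1.1.4 put it slightly differently: "Patients who drop out prior to be evaluable for DLT during the dose escalation will be replaced".

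The decision rules are written without reference to that population. Protocol 8.1 says that "if 2 or more patients experience a DLT at any dose level, further enrolment at that dose level and further dose escalation will cease". Protocol 8.5.5.1 and SAP 5.1.1.1 give the MTD as "defined as the highest dose level at which no more than 1 of 6 patients experiences a DLT during the DLT assessment window". Protocol 9.3 assigns analysis sets only to the PK and safety analyses. In the SAP the DLT population appears in its definition and in the disposition table. The SAP's one DLT table, by SOC and PT, belongs to the adverse event section of 6.1.1.2, where "All AEs summaries will be based on the Safety population". SAP 8.1.1.2 makes an ITT population the default for tables, but neither document defines one.

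**The concern.** A usual DLT-evaluable definition has two limbs: patients who had a DLT, and patients without one who received enough drug and were observed long enough. Only the second limb is written here, so the dose and follow-up requirements also fall on patients whose outcome is already known.

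The protocol itself foresees how such a patient could fail the dose requirement. Section 8.3.3 gives instructions that begin "In case of incomplete administration of study treatment because of the occurrence of treatment-related SAE/DLT". If that happens in Cycle 1 with less than 75% infused, the definition excludes the patient and the next sentence calls for a replacement. A death or loss to follow-up after a DLT but before Day 21 fails the other requirement.

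The primary endpoint is a count out of 6, so one patient can change the decision. An exclusion of this kind removes DLTs and never adds them.

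**Working it through.** **The plan's own figures.** The planned total adds up (100 + 22 = 122), but it is a first estimation with no error rate or operating characteristic for the MTD rule. There is no stated figure to reproduce.

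**Conflict at one dose level.** Suppose 7 patients are dosed at a level. One has a DLT with the infusion stopped below 75% and is replaced; one of the other 6 has a DLT.

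- By the DLT population: 1 of 6, which meets the MTD definition.
- By the stopping rule as written: 2 patients with a DLT, so enrolment and escalation at that level stop.

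**Size if the population definition governs.** The inputs are the 3+3 rule from Protocol 8.1 and two assumptions: the true DLT rate *p*, and the share *f* of DLTs that leave the patient non-evaluable. The documents give neither.

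- DLT rate among counted patients: p' = p(1 − f)/(1 − pf), with q = 1 − p'.
- Chance of clearing a level (0 of 3, or 1 of 3 then 0 of 3): q³ + 3p'q⁵.
- With r = pf, chance of clearing a level although 2 or more dosed patients had a DLT: q³[1 − (1 − r)³ − 3r(1 − r)³] + 3p'q⁵[1 − (1 − r)⁶].

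Worked case, p = 0.33 and f = 0.05:

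- p' = 0.3135/0.9835 = 0.3188 and q = 0.6812.
- q³ = 0.3162 and 3p'q⁵ = 0.1403, so the level clears with probability 0.456.
- r = 0.0165. The second probability is 0.3162 × 0.0016 + 0.1403 × 0.0950 = 0.0138.

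| True DLT rate | f | p' | Level cleared | Cleared with 2 or more DLT patients dosed |
|---|---|---|---|---|
| 20% | 0 | 0.2000 | 70.9% | 0 |
| 20% | 2% | 0.1968 | 71.6% | 0.5% |
| 20% | 5% | 0.1919 | 72.6% | 1.2% |
| 20% | 10% | 0.1837 | 74.4% | 2.4% |
| 33% | 0 | 0.3300 | 43.4% | 0 |
| 33% | 2% | 0.3255 | 44.3% | 0.5% |
| 33% | 5% | 0.3188 | 45.6% | 1.4% |
| 33% | 10% | 0.3071 | 48.0% | 2.9% |

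A simulation with explicit replacement (400,000 runs per point, p = 0.33) gave 43.5%, 44.3%, 45.7% and 48.1% for clearing a level. For clearing with 2 or more DLT patients it gave 0.51%, 1.42% and 2.87% at f = 2%, 5% and 10%.

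**The case against.** The strongest reply is that no operative rule passes through the DLT population. Expansion, stopping and the MTD all count patients who experience a DLT, and the CRC reviews all available data before each escalation (Protocol 8.7). Applied as written, these rules keep the patient and there is no bias. DLT-type toxicities from later cycles also inform the MTD (Protocol 8.5.5.1, SAP 5.1.1.1), so a plan that looks beyond Cycle 1 is unlikely to intend discarding a Cycle 1 DLT. Protocol 9.1 ties replacement to drop-out before evaluability, and a patient with an observed DLT has already supplied the outcome.

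The route is also narrow. Most DLT criteria need days to be met and cannot arise during a 3-hour infusion. Section 8.3.3 is a drug-accountability note; it is not limited to Cycle 1 and gives no fraction of the dose. No infusion-related reactions were seen up to 1.60 mg/kg (Protocol 6.3), and interrupted infusions may be resumed (8.4.4). Adverse events are recorded to at least 28 days after the last dose (8.6.2), and patients stopped for safety are followed (8.6.8). The one reported DLT, febrile neutropenia at 1.60 mg/kg, was counted and the cohort was expanded to six (6.2.3). A dropped DLT would still show in the SAP's table on the Safety population.

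All of this stands, and it points to a low *f*. It does not remove the gap. Evaluability is defined only by the two conditions, so the wording in 9.1 leads back to them. The later-cycle provision does not say that a patient with a Cycle 1 DLT stays evaluable. A permanently stopped infusion or a death before Day 21 remains uncovered. The CRC Charter and Data Review Plan are separate documents that were not available and may settle the matter, but the protocol and SAP should still say who is counted for their own primary endpoint.

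**Conclusion.** The concern holds. All three definitions lack the clause, and neither document names the set for the MTD count, so two readings are open and they can disagree at the same dose level. Under the escalation rules as written, *f* = 0 and nothing changes. Under the population definition the bias is small and always towards calling a dose safe. At f = 2% the chance of clearing a level rises by 0.7 percentage points at a 20% DLT rate (71.6 − 70.9) and 0.9 at 33% (44.3 − 43.4). At f = 10% it rises by 3.5 and 4.6 points. These sizes rest on assumed values of *p* and *f*. Nothing in the documents shows that the wording has affected a decision so far. It should be fixed because it bears on the primary endpoint of a first-in-human study and the correction costs almost nothing.

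**What to change.** In Protocol 9.2, the synopsis and SAP 6.1.1.3, define the DLT population as:

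- (a) every dosed patient with a DLT in the assessment window, whatever share of the dose or follow-up was completed; plus
- (b) patients without a DLT who received at least 75% of the first dose and completed 21 days of safety follow-up.

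State that only patients without a DLT can be declared non-evaluable and replaced, and align the replacement sentences in Protocol 8.2.3 and 9.1 and SAP 6.1.1.4. Name this set for the escalation and MTD counts. Check that the CRC Charter and Data Review Plan use the same definition. The DLT table by SOC and PT may stay on the Safety population.

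The cost is one sentence in each place. The observed DLT rate may be slightly less favourable, and a cohort may hold one patient more than 3 or 6. No dose, DLT criterion or escalation threshold changes.
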